### **VIII. Protection against risks.**

**VIII.a. Hypoglycemia.** We expect that <10% of subjects will experience episodes of hypoglycemia. To minimize the risk, outpatient dose of insulin will be reduced by 20% on admission; and insulin naïve patients  $\geq 70$  years of age and/or with an eGFR  $< 60$  will be started at a TDD of 0.3 U/kg/day.

**VIII.b. Severe hyperglycemia.** Patients with persistent hyperglycemia ( $\geq 3$  consecutive BG readings  $> 260$  mg/dL or a mean daily BG  $\geq 260$  mg/dL) after the 1st day of treatment will be considered as treatment failure and will be switched to continuous insulin infusion if needed. Patients randomized to group 1 will receive insulin supplements for BG  $> 140$  mg/dL. Those randomized to group 2 will receive insulin supplements only when BG  $> 260$  mg/dL. We anticipate that less than 1% of patients will experience severe hyperglycemic episodes (BG  $> 350$  mg/dL).

### **VIII.c. Data and Safety Monitoring Plan (DSMP).**

The DSM committee will review unblended data on safety, treatment compliance, and evaluate the efficacy of the intervention being studied in this clinical trial. The DSMC will meet at 6-month intervals and report on study progress to the IRB.

**VIII.d. Interim Analysis and Stopping Rules.** An independent data safety and monitoring board will assess hospital complications and severe hypoglycemic events. The trial will be stopped if there is evidence beyond a reasonable doubt of a difference between groups on hospital complications (two-sided alpha level,  $< 0.01$ ) or if severe hypoglycemic events ( $< 40$  mg/dL) are  $> 20\%$ .

**IX. Timetable.** Our research team has extensive experience in conducting prospective RCTs comparing different insulin regimens in T2DM. We have postdoctoral fellows and research coordinators in the 2 hospitals affiliated with Emory University. Based on our experience, we can recruit 4 to 8 medical/surgical patients with T2DM per week, thus we anticipate completing recruitment in 12 to 18 months.

**X. Potential Benefits to the Subject.** We believe that all subjects will benefit greatly from this study. Intensified BG monitoring and glycemic control may significantly reduce hospital complications associated with hyperglycemia and hypoglycemia.

**XI. Potential Benefits to Society.** This study will provide clinically useful information by determining benefits of insulin supplementation prior to meals in improving glycemic control and in reducing hypoglycemia in insulin treated patients with T2DM.

**XII. Risk/Benefit Assessment.** Insulin therapy is the mainstay of diabetes management in medical and surgical patients with diabetes. There are no prospective, randomized studies to assess the benefits of insulin supplementation in non-ICU patients with T2DM treated with a basal bolus regimen. Basal bolus regimen has been shown to be effective in general medicine and surgery patients; however, some patients may experience mild and moderate hypoglycemia.

**XIII. Therapeutic Alternatives.** Patients can be treated with oral pharmacological agents and several different types of insulin are currently available at Grady Hospital and Emory University Hospital and other institutions for the treatment of T2DM.

**XIV. Inclusion of women.** We anticipate that ~50% of the study subjects will be female. No patients under the age of 18 and no pregnant women will be included in the study. Absence of pregnancy must be demonstrated by blood or urine testing if clinically indicated (i.e., female subjects of child bearing potential).

**XV. Inclusion of minorities.** Patients will not be excluded based on race or ethnic origin. We anticipate that approximately one-third of patients will be African Americans, Hispanics, and Caucasians.

**XVI. Inclusion of children.** No patients under the age of 18 will be recruited in this study.

**XVII. Confidentiality.** Informed consent will follow the procedure of Emory University Institutional Review Board. Every potential participant will be informed in writing and verbally with the important key points of the study. One of the investigators or research coordinators will obtain a witnessed informed consent prior to inclusion of a patient into the study. Data collection records with personal identifiers will be stored in locked file cabinets. Presentation of the study results at regional or scientific meetings or in publications will not identify subjects. Access to research and confidential records will be limited to clinical investigators, coordinators, and the IRB at Emory University.

**XVIII. Payment for Participation.** Participation in this study is voluntary. Patients will receive twenty dollars (\$20.00) prior to discharge. If a participant should stop participation before completion, the payment will be prorated at \$10.00 per day to a maximum of twenty dollars (\$20.00).

**XIX. Financial Obligation.** No additional cost to patients or to the institution will be incurred for research purposes. Glargine, detemir, aspart and lispro are formulary drugs and represent the standard of care in our institutions. Glargine detemir, aspart and lispro, syringes, glucose meter and strips, and oral antidiabetic drugs will not be provided as part of the study.

**XX. Research Injuries.** If a patient is injured because of taking part in this study, [name] along with the Emory Co-Investigators with the medical facility will make medical care available to the patient at patient's own cost. Financial compensation for such things as lost wages, disability or discomfort due to an injury related to the study is not available.

**XXI. Financial Conflict of Interests.** None of the investigators in this study have any outside activities that may represent a conflict of interest. None of the investigators have an economic interest in an outside entity, or act as officers, directors, employees or consultants with such an entity, whose financial interest may be affected by this research study.

**XXII. Informed Consent.** After identification of eligible patients these individuals will be provided basic information regarding the study and, if interested, they will then be screened by research staff using the inclusion/exclusion criteria delineated elsewhere in this protocol. The consent form, potential risks and benefits, and the rights of research participants will be explained to the participant by the investigators or research coordinator. Individuals will be asked if they have any questions, and if present, questions will be answered by research staff. The principal investigator will also be available at all times to answer questions that participants may have during the consent procedure or during the time a participant is enrolled in the study. The consent form will be completed in accordance with the IRB guidelines of Emory University. A signed copy of the consent form will be provided to the participant and a copy will be placed in the file that is maintained for each participant in the study office.

**XXIII. Medical Device Research.** Not applicable.

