Several RCT have shown that hypoglycemia occurs in 12% and 33% of general medicine and surgery patients treated with basal bolus insulin regimens, respectively (6; 7; 11; 12). In the RABBIT-surgery trial (6), general surgery patients were treated with a total insulin dose of 0.5 unit/kg/day, given half as glargine once daily and half as glulisine before meals. A total of 17% of patients had a BG <70 mg/dL and 4% had a value <40 mg/dL. More recently, the Basal Plus trial (11) reported that 12% and 5% of patients treated with basal bolus with glargine and glulisine or with basal plus correction (supplements), respectively, had a BG <70 mg/dL and

only 1% had a BG <40 mg/dL. In the DEAN trial (12), a basal-bolus regimen using detemir and aspart vs. NPH and regular insulin reported that ~one-third of patients had a BG < 60 mg/dl (12). Minimizing hypoglycemic events is of major importance in hospitalized patients because it has been shown to be an independent risk factor of poor outcome (23-25). It is not known, however, if the use of insulin supplements may have an impact on the overall rate of hypoglycemia in patients treated with basal bolus insulin regimen.

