In a recently completed study (POC) (13), we found that not correcting mild to moderate hyperglycemia at bedtime did not change fasting daily glucose levels (Figure 6). Further, there were no changes in mean daily glucose, pre-meal glucose or hypoglycemic events (Figure 7). In this study, TDD of insulin was 42 units/day. Of this, only 6 units/day was required as a supplemental dose.

**Frequency of hypoglycemia and hyperglycemia during basal insulin treatment.** The frequency of mild hypoglycemia (BG<70 mg/dl) and severe hypoglycemia (BG<40 mg/dl) at bedtime among 2,377 patients recruited in different randomized control trials conducted by our research team is less than 1.5% and 0.5%, respectively. The frequency of hypoglycemia is low in comparison to patients treated with sulfonylureas (26). Similarly, the frequency of severe hyperglycemia (BG>400 mg/dl) is remarkably low (0.08%) among insulin treated patients with T2DM (6; 7).

*In summary*, during the past decade our research group has provided novel and important information to guide health care providers in inpatient management of patients with hyperglycemia and diabetes. Our preliminary data indicate that the use of basal insulin alone or in combination with rapid-acting insulin analogs (basal bolus regimen) in non-ICU patients with T2DM improves glycemic control and reduces the rate of hypoglycemia. In addition, our studies

have shown that BG values remain relatively constant during the day and that the need for supplemental insulin is low in comparison to the TDD of insulin required.

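### Read as a share of patients, the 20% stop for severe hypoglycemia is five to twenty times the protocol's own BG <40 rates and would very rarely fire if the higher rate doubled or tripled

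*Combined protocol and SAP*

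**What the plan says.** Section VIII.d (Interim Analysis and Stopping Rules) has two triggers. One is a between-group difference in hospital complications at a two-sided level below 0.01. The other applies "or if severe hypoglycemic events", defined by BG <40 mg/dL, are above 20%. The section does not say 20% of what (patients, events, readings or hypoglycemic episodes), whether the arms are taken separately or together, or where the figure comes from.

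The protocol gives these rates for comparison:

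- Background, general surgery basal bolus trial: "A total of 17% of patients had a BG <70 mg/dL and 4% had a value <40 mg/dL".
- Background, Basal Plus trial: "only 1% had a BG <40 mg/dL". The sentence covers the basal bolus and basal plus arms together.
- Preliminary Data, bedtime frequencies of BG <70 and BG <40 among 2,377 patients in the group's trials: "is less than 1.5% and 0.5%, respectively".
- VIII.a: "We expect that <10% of subjects will experience episodes of hypoglycemia". Section VI defines hypoglycemia as BG <70 mg/dL.
- Background, any-grade hypoglycemia in earlier basal bolus trials: 12% and 33%.

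On the timing of looks, VIII.c says "The DSMC will meet at 6-month intervals" and the Timetable says "we can recruit 4 to 8 medical/surgical patients with T2DM per week".

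**The concern.** The Research Objectives call hypoglycemia an independent marker of mortality, and the Background calls it an independent risk factor for poor outcome. The trial's hypothesis is itself partly about hypoglycemia. The complications trigger does not cover it, because the complications listed in IV.b do not include it. The 20% figure is therefore the only numeric trial-level limit on severe hypoglycemia.

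If that limit lies far above any rate the investigators have seen, a marked worsening can pass beneath it. The board and the IRB may then credit the rule with more protection than it gives.

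**Working it through.** **Plan's own figure.** The 20% has no derivation or operating characteristics in the documents, so there is nothing to reproduce. The check is how the limit behaves at rates anchored on the protocol's own figures.

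**Assumption.** The 20% is read as the share of patients with at least one BG <40, because the 4% and 1% in the Background are shares of patients.

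**Ratios.** 20/4 = 5; 20/1 = 20. Against the any-grade expectation in VIII.a, 20/10 = 2, or more since that figure is an upper bound. In the trial with the 4% severe rate, any BG <70 occurred in 17%, so the limit for the severe grade exceeds that trial's any-grade rate.

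**Patients available at a look.** Six months is about 26 weeks. At 4 to 8 patients per week this is 104 to 208 in total, or 52 to 104 per arm. Full enrolment is 125 per arm (IV.c).

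**Chance that the rule fires.** With r the smallest count strictly above 20% of n, and X binomial(n, p), the chance is P(X ≥ r). The rates are the 4% figure multiplied by 2, 3 and 4, then 20% itself.

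| Patients in one arm | Count needed | True 8% | True 12% | True 16% | True 20% |
|---|---|---|---|---|---|
| 52 | 11 | 0.24% | 4.2% | 20% | 47% |
| 104 | 21 | 0.007% | 1.1% | 15% | 52% |
| 125 | 26 | <0.001% | 0.35% | 9.3% | 45% |

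An even chance of firing needs a true rate near 20%. If the 1% figure is doubled or tripled (2-3%), the chance is below 0.0001% at every size shown.

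**Sensitivity to the arm.**

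- Both arms at 12%, either able to trigger: 1 − (1 − 0.0421)² = 8.2% with 52 per arm, 2.3% with 104, 0.7% with 125.
- Pooled, both arms at 12%: 0.01% with 250 patients.
- Pooled, one arm at 12% and the other at 4%: 0.005% with 104 patients in total.

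**Sensitivity to the unit.** As a share of patients with hypoglycemia, the surgery trial gives 4/17 = 24%, already above 20%. Basal Plus gives about 1/12 = 8% (basal bolus arm any-grade rate). On this reading the rule could fire at rates already reported, so the conclusion depends on the unit.

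**A trigger tied to 4%, for illustration only.** Let the trigger be an exact (Clopper-Pearson) one-sided 95% lower limit above 4% in an arm.

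| Patients in one arm | Count needed | True 4% | True 8% | True 12% |
|---|---|---|---|---|
| 52 | 6 | 1.7% | 23% | 60% |
| 104 | 9 | 2.4% | 45% | 89% |

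At 125 per arm the count is 10, but enrolment is then complete and a pause would have no effect.

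**Overall false-alarm chance at a true 4%.** With looks at 52 and 104 per arm, the chance that one arm triggers at either look is 3.4%; for two arms, 1 − (1 − 0.034)² is about 7%. With looks at 52 and 125 it is 3.9% per arm, and 1 − (1 − 0.039)² is about 8%.

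**The case against.** *The rule has no unit, so its level cannot be judged.* This stands in part. The finding holds for a share of patients, which matches the unit of the cited rates. A reader might infer that the limit is too high however the denominator is defined; the 24% above shows that the documents do not support that.

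*A limit that is rarely reached is not a limit that cannot be reached.* This stands. A reader might infer that the rule could never respond to a tripling. The table does not support that: one arm of 52 at 12% fires 4.2% of the time, and at 16% the chance is 20%.

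*Patients have other protection.* This also stands. The VIII.c committee reviews safety data by group every six months and reports to the IRB, and nothing confines it or the VIII.d board to the 20% figure. The insulin adjustment rules respond to each unexplained BG <70, and IV.f gives hypoglycemia orders. To infer that severe hypoglycemia goes unmonitored would be wrong. None of these, however, is a numeric trial-level limit.

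*The comparators are selective.* Partly right. The <10% in VIII.a sits below the 12% and 33% any-grade rates in the Background, and the bedtime figure is not a rate per hospital stay. The five-fold and twenty-fold ratios use neither.

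*No worsening is expected.* The protocol hypothesizes that withholding correction may reduce hypoglycemia, so the documents give no reason to predict a doubling in Group 2. A safety limit is meant for what is not predicted, and it covers both arms.

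*The illustrative trigger is itself weak early on.* True: with 52 per arm it misses a doubling 77% of the time (100 − 23). It still responds far more often than the present rule.

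**Conclusion.** The concern holds with two conditions attached. Read as a share of patients, the 20% limit is five and twenty times the BG <40 rates the protocol reports, and at least twice its expectation for any hypoglycemia. On that reading it is very unlikely to fire if the 4% rate doubled (at most 0.24% per arm at the sizes checked) or tripled (at most 4.2% per arm).

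The first condition is the unit, which VIII.d does not state. The second is that the limit is a backstop to committee review and not the sole safeguard. The calculations also treat patients as independent and everyone enrolled by a look as evaluable. This is a weakness to correct in the monitoring plan; it does not show that the trial is unsafe.

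**What to change.** In VIII.d:

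1. State the unit (patients with any BG <40 mg/dL) and that it is assessed separately in each arm.
2. Reconcile the 20% with the 4% and 1% in the Background and the <10% in VIII.a, and give the reason for whatever level is kept.
3. Have the sponsor and the board set a review trigger tied to a stated reference rate. Print the patient counts and the chance of firing at one, two and three times that rate for 52 to 104 patients per arm.

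The 4% trigger worked out above shows the form such a table could take. Its reference rate and confidence level are for the sponsor and board to choose.

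The cost is a sentence or two and a small table, with no new data. The downside is an occasional unneeded board review: for the illustration, about 7-8% overall at a true 4% across two arms and two looks.

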## II. BACKGROUND AND CURRENT STATUS OF WORK IN THE FIELD.

**Inpatient Glycemic Control in non-ICU setting.** A large body of evidence suggests that in hospitalized patients with and without diabetes, the presence of hyperglycemia is associated with increased risk of complications and death (2-5; 15-20). Prospective RCTs in critical care patients have shown that aggressive glycemic control reduces short- and long-term mortality, multi-organ failure, systemic infections, and length of hospital and ICU stay [7, 9-11]. Similar complication reductions has been shown in patients admitted to general medicine and surgery services as well. In the non-ICU setting, practice guidelines for the management of hyperglycemia in patients with T2DM favor the use of physiologic (basal-nutritional-correction dose) insulin regimens over sliding scale regular insulin (SSRI) (4; 5). Several RCTs have shown that a basal bolus regimen improves glycemic control and reduces hospital complications in general medicine and surgery patients with T2DM (5-7; 21; 22).

Treatment with basal insulin glargine alone or in combination with rapid-acting insulin analogs before meals (basal bolus regimen) result in fairly constant BG values during the day (see preliminary data below). We have shown that with the exception of a small and non-significant rise in BG concentration before lunch (noontime), treatment with glargine insulin allows 24 hours of BG control with low rates of hypoglycemia, severe hyperglycemia and minimal requirement of insulin supplements (~5-9 U/day) (6; 7). In particular, our data indicate that BG concentration remains relatively constant during the evening with a low rate of severe hyperglycemia (0.1% of BG >400 mg/dl) despite minimal use of insulin supplements (see preliminary data). This small dose of supplemental insulin used in our previous studies raises the question of its necessity as part of a basal bolus regimen.

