##### **IV.b. Primary and Secondary Outcomes:**

The primary outcome of the study is to compare differences in mean daily BG levels between patients receiving insulin supplementation for correction of hyperglycemia (BG > 140 mg/dL) compared to those without insulin supplementation except for correction of severe hyperglycemia (BG > 260 mg/dL).

Secondary outcomes include differences between treatment groups in any of the following measures: 1) mean BG before meals, bedtime and 3 AM; 2) number of BG within target; 3) number of hypoglycemia (BG < 70 mg/dl); hyperglycemia (BG > 260 mg/dL during the day or BG>350 mg/dl at bedtime); 4) daily dose of insulin; 5) length of hospital stay and mortality; 6) hospital complications (nosocomial infections, pneumonia, bacteremia, respiratory failure, and acute kidney injury [rise of serum creatinine >0.5 mg/dL (or 50%) of baseline value]), 7) hypoglycemia symptom assessment in both groups.

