**BEDTIME. Give half of Supplemental Sliding Scale Insulin.**

Blood Glucose (mg/dL)	Sensitive	Usual	Resistant
<221	0	0	0
221-260	1	2	4
261-300	2	3	5
301-350	3	4	6
351-400	4	5	7
> 400	5	6	8

The patient's inpatient primary medical or surgical team may change insulin dose at their discretion in the presence of hypoglycemia (BG <70 mg/dL) or severe hyperglycemia (BG >350 mg/dL). In addition, the attending and/or study physician may consider using the total supplemental insulin dose, patient's nutritional intake, and results of BG testing to adjust insulin regimen.

**Blood glucose monitoring.** BG will be measured before each meal, at bedtime and/or 3 AM (or every 6 hours if a patient is not eating) using a glucose meter. In addition, blood glucose will be measured at any time if a patient experiences symptoms of hypoglycemia or if requested by the treating physician. The nursing staff or a research team staff will record all glucose readings in the hospital's blood glucose flow-sheet (electronic chart).

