**BEDTIME. Give half of Supplemental Sliding Scale Insulin**

Blood Glucose (mg/dL)	Sensitive	Usual	Resistant
< 260	0	0	0
261-300	2	3	5
301-350	3	4	6
351-400	4	5	7
> 400	5	6	8

The attending physician may change insulin dose as his/her discretion in the presence of hypoglycemia (BG <70 mg/dL) or severe hyperglycemia (BG >350 mg/dL). In addition, the attending and/or study physician may consider using the total supplemental insulin dose, patient's nutritional intake, and results of BG testing to adjust insulin regimen.

**Blood glucose monitoring.** BG will be measured before each meal, at bedtime and 3 AM (or every 6 hours if a patient is not eating) using a glucose meter. In addition, blood glucose will be measured at any time if a patient experiences symptoms of hypoglycemia or if requested by the treating physician. The nursing staff or a research team staff will record all glucose readings in the hospital's blood glucose flow-sheet (chart).

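### As worded, the glucose-check schedule may differ by arm: the 3 AM reading can be omitted in Group 1 but not in Group 2, although bedtime, 3 AM and hypoglycemia outcomes are compared between groups

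*Combined protocol and SAP*

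**What the plan says.** Each group has its own paragraph on blood glucose monitoring, placed after its bedtime supplement table.

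- Group 1: "BG will be measured before each meal, at bedtime and/or 3 AM (or every 6 hours if a patient is not eating".
- Group 2: "BG will be measured before each meal, at bedtime and 3 AM (or every 6 hours if a patient is not eating".

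The rest of the two paragraphs agrees in substance. Patients who are not eating are measured every 6 hours in both groups, and symptoms or a physician's request prompt an extra test in both.

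Section IV.b lists as between-group outcomes "mean BG before meals, bedtime and 3 AM" and "number of hypoglycemia (BG < 70 mg/dl", along with the number of readings in target. It names mean daily glucose as the primary outcome. The hypothesis under Research Objectives and Specific Aims is that correction doses, which Group 1 receives from a lower glucose level, may raise the risk of hypoglycemia.

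Section VIII.d stops the trial for a between-group difference in hospital complications, "or if severe hypoglycemic events" (below 40 mg/dL) exceed 20%. It does not say what the 20% is a share of, or whether it is checked per arm or pooled.

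**The concern.** Hypoglycemia here is found by measuring. If one arm has fewer scheduled measurements, the same underlying risk yields fewer recorded lows in that arm, and a between-group comparison mixes treatment effect with detection.

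The Group 1 sentence allows either bedtime or 3 AM to be dropped. The Group 1 supplement rules call for a dose decision at bedtime, so the reading more likely to be left out is 3 AM. That is when a low without symptoms is least likely to be found by other means.

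Three things would be affected:

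- the hypoglycemia comparison, in a direction that hides an excess in Group 1;
- the 3 AM mean in IV.b, which could not be estimated for Group 1 patients who are never measured then;
- the make-up of mean daily glucose, which would average different time points in the two arms.

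**Working it through.** **Scheduled readings per day, patient eating**

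- Group 2: 3 before meals + bedtime + 3 AM = 5.
- Group 1: 3 before meals + one or both of bedtime and 3 AM = 4 or 5.
- Largest shortfall: 1 of 5, or 20% of scheduled readings.

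**Effect on the share of patients with at least one low**

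The documents give no rate of lows at 3 AM, so this is an illustration. Assume that every scheduled reading carries the same independent risk, that true risk is equal in both arms, and that a missed low is not found in any other way. If p is the share of patients with at least one low on 5 readings a day, then with an average of k readings a day the share is

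1 − (1 − p)^(k/5),

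whatever the length of stay. Use k = 4 if one reading is missed every day, k = 4.5 if half are missed, and k = 5 if none are.

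The inputs for p are per-patient rates in section II. In the general surgery trial, "A total of 17% of patients had a BG <70 mg/dL and 4% had a value <40 mg/dL". In the basal bolus arm of the Basal Plus trial, 12% had a reading below 70 mg/dL. Treating these as rates on 5 readings a day is a further assumption.

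| Group 2 shows | Group 1, one missed daily | Group 1, half missed | Group 1, none missed |
|---|---|---|---|
| 17% (<70 mg/dL) | 1 − 0.83^0.8 = 13.8% | 1 − 0.83^0.9 = 15.4% | 17% |
| 12% (<70 mg/dL) | 1 − 0.88^0.8 = 9.7% | 1 − 0.88^0.9 = 10.9% | 12% |
| 4% (<40 mg/dL) | 1 − 0.96^0.8 = 3.2% | 1 − 0.96^0.9 = 3.6% | 4% |

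In patients, with 125 per group, the first row runs from 0.17 × 125 = 21.3 in Group 2 to 0.1385 × 125 = 17.3 in Group 1 at the far end. That is about 4 patients, produced by the schedule alone. In the last row it is 5 against 4.

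**Effect on counts**

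IV.b counts lows and readings in target, and section VII plans Poisson regression for discrete outcomes without mentioning the number of readings. Under the same assumptions, the expected count in Group 1 is up to 4/5 = 0.80 of that in Group 2 with no difference in risk. Adjusting for the number of readings would correct the count. It would not recover what happens at 3 AM.

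**Effect on mean daily glucose**

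If the 3 AM value lies d mg/dL below the mean of the other four, including it lowers the daily mean by d/5. For this to reach the 18 mg/dL margin in section VII, d would have to be 18 × 5 = 90 mg/dL. The effect on the primary outcome in IV.b is therefore likely to be modest. Mean fasting glucose, which section VII analyses, is taken before breakfast and is not affected.

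**The case against.** The strongest reply is that the Group 1 wording includes the Group 2 schedule as one of its options. A site can follow both sentences and measure both groups five times a day. Since IV.b compares 3 AM means between groups, the plan evidently needs that reading in both, and a drafting slip is at least as likely as an intended difference. This stands. A reader might infer that the trial schedules unequal monitoring by design, and the documents do not support that. What remains is that the operative instruction for Group 1 permits the omission and nothing else in the plan forbids it.

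Second, the far end of the range requires every eating Group 1 patient to miss a reading every day, with no low found otherwise. Symptom-prompted tests, tests on request and 6-hourly checks in patients not eating apply equally in both arms. The gap therefore concerns mainly symptom-free lows in patients who are eating, and could be nil. This also stands. In the other direction, the gap is larger if lows cluster at night.

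Third, under-detection would fall in the standard-of-care arm and so works against the investigators' own hypothesis about hypoglycemia. That is true, but a bias in a known direction is still a bias in a listed outcome.

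A reader might also infer that the stopping rule in VIII.d is unworkable. The documents do not support that. Per patient is the natural reading, since section VIII.a forecasts hypoglycemia by subject and section II reports values below 40 mg/dL by patient: 4% in one trial, and in another "only 1% had a BG <40 mg/dL". The share-of-readings figure in section II, "low rate of severe hyperglycemia (0.1% of BG >400 mg/dl", concerns hyperglycemia. At 1% to 4% the limit is not approached, and the monitoring committee sees unblinded data and so can look at each arm. Nor is a limit above the expected rate a contradiction.

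**Conclusion.** The point holds in a limited form. As worded, the plan permits four scheduled readings a day in Group 1 against five in Group 2 for patients who are eating, with the overnight reading the likely omission. It does so although IV.b compares bedtime, 3 AM and hypoglycemia outcomes in both groups.

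On the illustrative assumptions, an equal risk recorded as 17% in Group 2 would be recorded as anything from 13.8% to 17% in Group 1. These figures rest on equal and independent risk per reading and show scale only; they are not a forecast.

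The open denominator and arm in VIII.d are a clarification to make at the same time. They would not be a finding on their own.

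**What to change.** Reconcile the two blood glucose monitoring sentences (Group 1 and Group 2, section IV.d) with each other and with IV.b, so that the scheduled time points do not differ by arm. No particular schedule is proposed here; that is for the investigators.

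While editing, state in VIII.d whether the 20% is a share of patients and whether it is checked per arm or pooled. Do this before the committee sees unblinded events.

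The cost is a change of wording in two monitoring sentences and one clause. Depending on how the sentences are reconciled, at most one scheduled reading per patient-day changes in one group. Sample size and the planned analyses are unaffected.
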